#### Short Title :

A vasoconstriction test trial with a MC2-01 cream (ranking trial).

Sponsor Trial Number:	MC2-01-C4
Clinical Trial Phase:	Phase 1
Investigator:	[name] [name]
Co-Investigator:	[name] [name]
Clinical Trial Population:	Healthy subjects, males and females, aged 18 to 50 years old.
Clinical Trial Objectives:	The objective of this trial is to compare the vasoconstriction potential (skin blanching effect) of MC2-01 cream with Clobex 0.05% (clobetasol propionate) lotion, Betamethasone Dipropionate (Augmented) 0.05% (betamethasone dipropionate) cream, Triamcinolone Acetonide 0.1% (triamcinolone acetonide) cream, Locoid ® 0.1% (hydrocortisone butyrate) cream, Desowen ® 0.05% (desonide) cream and MC2-01 vehicle using the human skin blanching test (McKenzie-Stoughton's test).
Background:	Topically applied corticosteroids elicit a pharmacologic activity (blanching) viewed by many as being "vasoconstrictive" in nature. The skin blanching effect was first described by Mc Kenzie and Stoughton (1) in 1962. This pharmacodynamic response has been correlated with the clinical efficacy of the product in psoriasis (2) and used for years to determine the clinical potency of topical corticosteroid formulations and to classify them within the US topical steroid potency classification.
	MC2 Therapeutics has developed an innovative dermal pharmaceutical formulation containing calcipotriol (CAL) 0.005 % w/w (50 $\mu$ g/g) and betamethasone dipropionate (BDP) 0.064 % w/w (0.5 mg/g as betamethasone), MC2-01 cream to ease local application of pharmaceuticals and to significantly enhance local cutaneous penetration of the active ingredients.
	Currently marketed products are restricted to non-oil-based formulations as calcipotriol and betamethasone are characterized by having a potential incompatibility to exist together in an environment, since calcipotriol requires basic conditions to maintain stability while betamethasone requires acidic conditions.

CPCAD Nice	C P C A D
Clinical Trial Protocol MC2-01-C4	Final Approved Version 20/08/2018
	MC2-01 cream has been formulated using the PAD ™ Technology allowing sufficient protection of the drug substances from degradation during storage.
Clinical Hypothesis:	The blanching effect of the MC2-01 cream is expected to be lower than Clobex, not significantly different from Betamethasone Dipropionate (Augmented) cream and higher than the other references.

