# 5.2.2 Rational for the reference products

In the US potency ranking of commonly used corticosteroids, Group I is the super-potent category. Potency descends with each group to group VII, which is the least potent.

In a ranking assay, the active reference products must be selected to ensure an adequate bracketing to determine the topical corticosteroid potency class of the MC2-01 cream (CA/BDP). It should also demonstrate that the IMP is not different from the target class representative.

The active reference products are listed below including their steroid potency description and Group and Class according to the 7-point US classification system. Several US classification charts (13) (14) (15) (16) and the WHO classification (17) have been used for reference and selection.

Generic name	Group /Class	Potency	Brand name	Rational
Clobetasol propionate 0.05%	I	Ultra High/Super potent	Clobex ® lotion	Highest potent
Betamethasone dipropionate 0.05 %	II	High/Potent	Betamethasone Dipropionate (Augmented) cream	Representative of the target potency group and matching steroid for the IMP
Triamcinolone acetonide 0.1%	IV	Medium	Triamcinolone Acetonide cream	Representative of a medium group
Hydrocortisone-17- butyrate 0.1%	V	Medium	Locoid ® cream	Representative of a lower medium group
Desonide 0.05%	VI	Low	Desowen ® cream	Lowest potency used in psoriasis (face or folds)

Page 17/54

This document will be regarded as confidential and proprietary in nature and will not be disclosed to any third party without sponsors written consent

Clinical Trial Protocol MC2-01-C4

Final Approved Version 20/08/2018

Group: From Stoughton (13), the American Academy of Family Physicians (16) and World Health Organization Classification of Topical Corticosteroids (17).

Class: Potency of Topical Corticosteroids (USA classification) (14).

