#### 13.2.1 Primary pharmacodynamic criterion

The analysed variable will be the mean between the two readers at each evaluation time.

The results will be expressed by the mean values obtained at each assessment time by product/site.

MC2-01 cream will be compared with Clobex lotion, Betamethasone Dipropionate (Augmented) cream, Triamcinolone Acetonide cream, Locoid® cream, DesOwen cream and MC2-01 cream vehicle in terms of visual score of skin blanching 2 hours after a 16 hours application, using an ANOVA with subjects and treatments as factors. The mean of visual assessments obtained at the same time points from 2 independent trained readers will be used. In case of a significant treatment effect, estimates of treatment effect and 95% confidence interval of differences between reference products and MC2-01 cream will be calculated from the model without correction for multiplicity in the primary analysis. Correction for multiplicity using Dunnett's test will be used as secondary analysis. In case of significant deviation to the normal assumption, a non-parametric approach with Kruskall-Wallis test for the overall product effect and Wilcoxon's Sign Rank Test for the pairwise comparisons will be used.

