### 13.5 Number of subjects calculation

The null hypothesis for each pairwise comparison will be no difference in the human skin blanching test :

H0: ∆ = 0,

where  $\Delta$  is the mean difference in visual score between test sites with the compared treatments. The standard assumptions of normality and independence will be used.

According to previous vasoconstriction trial performed by CPCAD, a maximal standard deviation for the difference of 0.65 is assumed.

Using a paired t-test, a two-sided significance level of 5%, with 30 complete subjects, the probability of detecting a difference of 0.5 units assuming a standard deviation for the difference of 0.65 is 98%.

MC2-01 cream will be compared to the five steroid-containing reference products giving at least 92% (0.98) power to obtain 5 significant differences if the true difference with each reference product is at least 0.5 int. MC2-01 cream will also be compared to the matching MC2-01 cream vehicle, but that will have negligible impact on the overall power assuming a difference of at least 1 point between both products.

A total of 36 subjects will be randomized in this trial in order to obtain at least 30 completed evaluable subjects.

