## 5.2 . Analysis of pharmacodynamic effect (blanching)

#### 5.2.1 Primary pharmacodynamic criterion

The analysed variable will be the mean between the two readers at each evaluation time.

The results will be expressed by the mean values obtained at each assessment time by product/site.

MC2-01 cream will be compared with Clobex® lotion, Betamethasone Dipropionate (Augmented) cream, Triamcinolone Acetonide cream, Locoid® cream, DesOwen® cream and MC2-01 cream vehicle in terms of visual score of skin blanching 2 hours after a 16 hours application, using an ANOVA with subjects and treatments as factors.

Some minor changes in the protocol statistical methods have been decided and reported in the SAP to improve the data analysis of the primary criterion.

The protocol planned that In case of a significant treatment effect, estimates of treatment effect and 95% confidence interval of differences between reference products and MC2-01 cream will be calculated from the model without correction for multiplicity in the primary analysis and that correction for multiplicity using Dunnett's test will be used as secondary analysis. In case of significant deviation to the normal assumption, a non-parametric approach with Kruskall-Wallis test for the overall product effect and Wilcoxon's Sign Rank Test for the pairwise comparisons will be used

The present Statistical Analysis Plan states that In case of a significant treatment effect, the comparisons between reference products and MC2-01 cream will be done from the model with correction for multiplicity using Dunnett's test directly in the primary analysis. For each fitted model, residual plots will be used to check the model assumptions. If there is an obvious deviation to these assumptions, the analysis will be done on the rank-transformed data.

The data will be also presented graphically by treatment using boxplot of visual assessment of skin blanching.

Statistical Analysis Plan MC2-01-C4 / CPCAD CPC-3530 Version 2.0 dated 05-Dec-2018 Page 14/16

The results will be presented as follows:

	MC2-01 cream (n=XX)	Clobex® lotion (n=XX)	Betamethasone Dipropionate (Augmented) cream (n=XX)	Triamcinolone Acetonide cream (n=XX)	Locoid® cream (n=XX)	Desowen® cream (n=XX)	MC2-01 cream vehicle (n=XX)
N Mean±SD Median (Min,Max)							
p-value a (treatment comparison versus MC2-01 cream)	-						

a: method used for multiple comparisons

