#### 5.4 General principles

All tests will be two-sided and the 0.05 probability level will be chosen to declare significance. The analysis will be performed using the R-Software version 3.3.2

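### Putting the augmented betamethasone dipropionate pair inside the SAP's primary Dunnett correction favours the non-significant result hoped for on that pair, by 14 to 24 points for true differences of 0.2 to 0.4 units

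*SAP*

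**What the plan says.** The Clinical Hypothesis in the protocol synopsis expects blanching with MC2-01 cream to be below Clobex, "not significantly different from Betamethasone Dipropionate (Augmented) cream and higher than the other references". Protocol 5.2.2 gives the middle comparison a special role in fixing the potency class: "It should also demonstrate that the IMP is not different from the target class representative".

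Protocol 13.2.1 fits an ANOVA with subject and treatment factors. If the treatment effect is significant, estimates and 95% confidence intervals for the differences "will be calculated from the model without correction for multiplicity in the primary analysis". Dunnett's test is secondary.

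SAP 5.2.1 describes its departures from the protocol as minor and reverses that order: "the comparisons between reference products and MC2-01 cream will be done from the model with correction for multiplicity using Dunnett's test", now in the primary analysis. No pair is exempted. The results table has one p-value row, labelled "treatment comparison versus MC2-01 cream", with a column for each of the five steroid references and one for the vehicle. It has no row for differences or their confidence intervals. SAP 5.4 adds: "All tests will be two-sided and the 0.05 probability level will be chosen to declare significance".

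The size of the Dunnett family is not quite explicit. The table points to six comparisons. The sentence speaks of reference products, and the treatment table (SAP 3.5) lists the vehicle as an investigational product, so five is a possible reading.

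**The concern.** Dunnett's procedure limits the chance of wrongly declaring a difference somewhere in the family. That is the relevant error for the pairs where the sponsor expects and wants a difference: Clobex, triamcinolone, Locoid, Desowen and the vehicle. For augmented betamethasone dipropionate the relevant error is the reverse, namely missing a real difference and reporting the two creams as alike. Raising the threshold on that pair can only make the hoped-for result more likely, so a step that looks conservative works the other way there.

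What is at stake is the comparison that places MC2-01 in its target class. The SAP does not mention this effect. It also no longer plans the unadjusted interval that would show how large a difference the data leave open.

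**Working it through.** **Inputs.** Protocol 13.5: SD of the paired difference 0.65 (described as maximal), 30 completers, difference 0.5 units, two-sided 5%. SAP 5.2.1: two-way ANOVA, seven treatments, MC2-01 as common comparator. Error degrees of freedom: (30 − 1) × (7 − 1) = 174. Assumed: normal scores and the same SD of the difference for every pair. The overall treatment test is ignored, because large Clobex and vehicle differences would make it significant almost always.

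**The plan's own figure.** For a paired t-test on those inputs, Protocol 13.5 states that "the probability of detecting a difference of 0.5 units assuming a standard deviation for the difference of 0.65 is 98" per cent. The noncentral t with 29 df gives 98.3%, so the stated power reproduces.

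**Thresholds.** The standard error of a difference is 0.65/√30 = 0.1187. The unadjusted critical value is t(0.975, 174) = 1.974. The two-sided Dunnett value c solves P(max|T| ≤ c) = 0.95 for equicorrelated t variables (correlation 0.5, 174 df):

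| Family | Critical value | Per-pair alpha | Smallest significant observed difference |
|---|---|---|---|
| Unadjusted | 1.974 | 5.0% | 1.974 × 0.1187 = 0.234 |
| Dunnett, 5 comparisons | 2.536 | 1.2% | 2.536 × 0.1187 = 0.301 |
| Dunnett, 6 comparisons | 2.592 | 1.0% | 2.592 × 0.1187 = 0.308 |

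Monte Carlo for six comparisons gives 2.591.

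**Chance of non-significance on this pair.** For a true difference δ the noncentrality is δ/0.1187, and the chance is P(|T| ≤ c) from the noncentral t with 174 df:

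| True difference | Unadjusted | Dunnett (6) | Rise, points |
|---|---|---|---|
| 0 | 95.0% | 99.0% | 4.0 |
| 0.10 | 86.6% | 95.8% | 9.1 |
| 0.20 | 61.2% | 81.5% | 20.3 |
| 0.25 | 44.6% | 68.3% | 23.7 |
| 0.30 | 29.0% | 52.4% | 23.4 |
| 0.40 | 8.2% | 21.9% | 13.7 |
| 0.50 | 1.3% | 5.4% | 4.1 |

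Rises are taken before rounding.

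**Sensitivity.**
- Five comparisons: rises of 18.8 points at 0.2, 21.2 at 0.3 and 12.1 at 0.4.
- All 36 randomized subjects evaluable, six comparisons: the largest rise is again 24 points (36.8% to 60.8% at 0.25).
- Smaller SD (assumed values), 30 completers: at a difference of 0.2, 41.3% to 65.3% with SD 0.5 and 22.3% to 44.1% with SD 0.4. The affected band moves towards zero: at 0.3 with SD 0.4 the figures are only 1.7% and 6.6%.

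**Whole hypothesised pattern.** The documents give no expected gaps for the other pairs, so these simulations rest on assumed ones. The deficit is the amount by which MC2-01 falls short of augmented betamethasone dipropionate. The figures are the chance that all six pairs come out as hypothesised.

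| Assumed gaps (Clobex, triamcinolone, Locoid, Desowen, vehicle) | Deficit | Unadjusted | Dunnett (6) |
|---|---|---|---|
| 0.5, 0.5, 0.8, 1.3, 1.8 | 0 | 93% | 89% |
| same | 0.10 | 85% | 86% |
| same | 0.30 | 28% | 47% |
| 0.4, 0.4, 0.6, 1.0, 1.5 | 0 | 81% | 57% |
| same | 0.20 | 52% | 48% |
| same | 0.30 | 23% | 30% |

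The sign of the change depends on the gaps and on the deficit, because Dunnett also makes the other five comparisons harder.

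**The case against.** The strongest reply is that the effect is confined to a band. At true equality the correction adds 4 points. At 0.5 units, the only effect size the protocol names, the Dunnett test still finds the difference 94.6% of the time. The documents do not say that 0.2 to 0.4 units matters clinically, and readers score in half units at the finest. All of this stands, and it rules out saying without qualification that the pair becomes much easier to pass.

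A reader might also infer that the SAP tilts the trial as a whole towards the sponsor's hypothesis. The documents do not support that. The correction costs power on the five pairs where a difference is wanted, and with modest assumed gaps it lowers the chance of the full pattern at equality and at a 0.2 deficit.

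Nor do they support saying that a real deficit would be hidden. The SAP discloses the change openly, and its table and boxplots show each product's mean and distribution. What is missing is the interval for the difference.

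It can also be said that no formal pass rule exists. The hypothesis is worded as an expectation, and Protocol 13.5 powers for five significant differences, this pair included. That is a fair observation about an inconsistent protocol. But Protocol 5.2.2 says the assay should demonstrate no difference from the class representative, and nothing in either document makes a significant difference on this pair the desired outcome under the stated hypothesis.

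Finally, the deeper weakness is the absence of a similarity margin, which exists with or without Dunnett: unadjusted, a true difference of 0.3 still passes 29% of the time. That is correct, and it limits what the fix can achieve. It does not justify loosening the only test the plan applies to this pair.

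**Conclusion.** The point holds in limited form and is a should-fix. SAP 5.2.1 places the one pair whose hoped-for result is non-significance under a correction that can only favour that result. The chance of non-significance rises by about 14 to 24 points for true differences of 0.2 to 0.4 units, and by about 4 points at equality and at 0.5 units.

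These figures assume SD 0.65, 30 completers, a common SD across pairs and six comparisons. With five comparisons the rises are slightly smaller and the direction is the same. A smaller SD shifts the band towards smaller differences. No general statement can be made about the whole hypothesised pattern, because it depends on gaps that the documents do not give.

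The lack of a margin, and so the inability of a non-significant test against zero difference to show similarity, is a separate issue that this point does not resolve.

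**What to change.** In SAP 5.2.1 and its results table, take the augmented betamethasone dipropionate pair out of the Dunnett family. Report for it, from the same ANOVA, the estimated difference, the unadjusted two-sided 5% test and the unadjusted 95% confidence interval, as Protocol 13.2.1 planned. Keep Dunnett for the comparisons where a difference is claimed (Clobex, triamcinolone, Locoid, Desowen, vehicle), and state how many comparisons the family contains. If a difference on the betamethasone pair were ever to be claimed as a finding in its own right, it would need its own multiplicity protection.

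The cost is a sentence or two of SAP text, a table row for the estimate and interval, and a footnote; no new data are needed. At true equality the chance of a non-significant result on this pair falls from 99% to 95%. The other five comparisons gain slightly, with the critical value going from 2.59 to 2.54. Under the first set of assumed gaps, the chance of the full pattern goes from 89% to 87% at equality and from 47% to 25% at a 0.30 deficit.

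### The expected potency pattern is never made a decision rule, and six-way Dunnett is stricter than a bracket needs, cutting the chance that all four directional comparisons succeed from about 95% to 82%

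*SAP*

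**What the plan says.** Three places in the protocol describe a joint result.

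- The Clinical Hypothesis in the synopsis says the blanching effect is "expected to be lower than Clobex, not significantly different from Betamethasone Dipropionate (Augmented) cream and higher than the other references".
- Section 5.2.2 says the active references must be "selected to ensure an adequate bracketing to determine the topical corticosteroid potency class of the MC2-01 cream". It adds that the trial should show no difference from the target class representative, which its table identifies as the Class II betamethasone cream.
- Section 13.5 gives the power for obtaining all five steroid differences together.

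The statistical sections test one pair at a time. Protocol 13.5 states: "The null hypothesis for each pairwise comparison will be no difference in the human skin blanching test". Protocol 13.2.1 fits an ANOVA with subject and treatment as factors. It leaves the primary comparisons uncorrected and makes Dunnett secondary. SAP 5.2.1 keeps the model but says the comparisons with MC2-01 "will be done from the model with correction for multiplicity using Dunnett's test directly in the primary analysis", and calls its changes to the methods minor. Its results table ends in a row of p-values. SAP 5.4 adds: "All tests will be two-sided and the 0.05 probability level will be chosen to declare significance". The SAP does not repeat the clinical hypothesis or the power calculation.

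**The concern.** Six p-values do not assign a potency class unless the plan says how to combine them. Two results show the difficulty. If MC2-01 is not significantly different from both Clobex and the Class II cream, the table is compatible with Class I or Class II. If it is not significantly different from both the Class II cream and triamcinolone, the table is compatible with Class II or Class IV. The statistical sections do not say what is concluded in either case.

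The multiplicity method also answers a different question. Dunnett limits the chance of at least one false difference among six. A bracket claim requires MC2-01 to be below Clobex and above triamcinolone, Locoid and Desowen, all at once. That is an intersection-union claim: it is false if any one component is false, so testing each component at unadjusted two-sided 5% already controls its error. A stricter threshold on each comparison then makes incomplete patterns more common. It also departs from the unadjusted level at which the trial was sized.

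**Working it through.** **Inputs**

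- Protocol 13.5: "Using a paired t-test, a two-sided significance level of 5%, with 30 complete subjects"; "a maximal standard deviation for the difference of 0.65 is assumed"; difference 0.5 units; vehicle difference at least 1 point.
- Assumed here: the same SD of the difference for every pair; 30 complete subjects, giving 29 × 6 = 174 error degrees of freedom; correlation 0.5 between contrasts because all share the MC2-01 site. The overall treatment test that precedes the comparisons and the rank-transform option are not modelled.

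**The plan's own figures**

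- SE = 0.65/√30 = 0.1187; noncentrality = 0.5/0.1187 = 4.21.
- Noncentral t with 29 df, two-sided 5%: power 0.9826. The protocol says "the probability of detecting a difference of 0.5 units assuming a standard deviation for the difference of 0.65 is 98" percent, so this reproduces.
- Five comparisons, treated as independent: 0.9826^5 = 0.916, which matches the stated 92% to rounding.

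**The SAP's threshold**

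- Unadjusted critical |t| with 174 df: 1.974.
- Two-sided Dunnett for six comparisons, correlation 0.5, 174 df: 2.592, about 0.0103 two-sided per comparison.
- Power for one difference of 0.5 under Dunnett: 94.6%. Product for five: 0.946^5 = 0.76.

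**Joint results**

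These come from 600,000 simulated trials. Each contrast is t = [(z_ref − z_MC2)/√2 + δ/SE]/s, where z_MC2 is common to all six and s² is chi-square(174)/174. The true gaps are 0.5 for each of the four directional references and 1.0 for the vehicle. The difference from the Class II cream is zero unless stated.

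| Event | Unadjusted 5% | Six-way Dunnett |
|---|---|---|
| Four directional comparisons all significant | 95.4% | 82.1% |
| Those four, and Class II cream not significant | 91.3% | 81.6% |
| All five steroids significant, Class II cream also 0.5 away | 94.3–94.5% | 78.1–79.5% |
| Any false difference, all seven products equal | 20.6% | 5.0% |
| False bracket: one required difference truly zero, the rest large | 2.5% | 0.5% |
| Class II cream not significant, true difference 0.3 | 29.0% | 52.4% |
| Class II cream not significant, true difference 0.5 | 1.3% | 5.4% |

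The range in the third row depends on whether the Class II cream lies above or below MC2-01. By the product method, about 38 completers would be needed to restore 92% for five differences under Dunnett.

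Under Dunnett, MC2-01 is non-significant against both Clobex and the Class II cream in about 5% of trials when the gap to Clobex is 0.5, 21% at 0.4 and 52% at 0.3. The corresponding result for the Class II cream and triamcinolone is nearly identical.

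**The case against.** The strongest reply is that the plan is coherent if read as six separate comparisons. The primary objective is only to compare blanching. The null hypotheses are pairwise, and Dunnett is the right correction for stand-alone statements about individual products: without it the chance of some false difference is about 21%. That stands. A reader might infer that Dunnett inflates the error of the bracket claim. It does not: it lowers it from 2.5% to 0.5%. The cost is power, not validity.

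A reader might also infer that no pattern is specified, or that the class is to be picked after the p-values are seen. The documents do not support either. The synopsis names the pattern and Protocol 5.2.2 names the target class in advance. What is missing is the step that carries the pattern into the analysis.

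Nor is the hypothesis one in which every comparison must be significant. It is mixed: four differences are expected, and the Class II cream is expected not to differ significantly. Only the power statement in 13.5 counts all five steroids as significant, which sits awkwardly with the synopsis.

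The inputs are also on the cautious side. The SD is described as maximal. Protocol 13.4 expects under 10% loss, and 36 × 0.9 = 32.4, so about 33 evaluable subjects are likely. If the gaps to triamcinolone, Locoid and Desowen were 0.5, 0.75 and 1.0 (an assumption), the full pattern under Dunnett would occur in about 89% of trials with 30 subjects and 92% with 33. Gaps of 0.3 or 0.4 lie below the design difference. At 0.3, non-significance against both Clobex and the Class II cream still occurs in about 27% of trials without correction, so much of that ambiguity is low power.

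**Conclusion.** The concern holds in this form: the expected pattern is stated but not adopted as the decision rule, and the primary correction is stricter than a bracket claim needs. At the plan's own inputs, with equal variances assumed, Dunnett costs about 13 points on the four directional comparisons (95% to 82%) and about 9 points on the full pattern (91% to 82%). The planned 92% for five differences becomes about 78 to 80%, and the SAP does not say so. With graded gaps or more completers the loss is smaller.

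The comparison with the Class II cream needs separate care. Protocol 5.2.2 wants it shown not to differ, but no margin is given, and Dunnett makes non-significance easier to reach: 52% against 29% at a true difference of 0.3. The four-way bracket does not settle this either. If MC2-01 were truly 0.5 below the Class II cream, 1.0 below Clobex, and 0.5, 0.75 and 1.0 above the three lower references, the unadjusted bracket would still pass in about 99% of trials. The bracket therefore supports a position between Clobex and triamcinolone, not Class II itself.

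**What to change.** In SAP 5.2.1:

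- State the primary decision: MC2-01 is concluded to lie between Clobex and triamcinolone acetonide if it is significantly lower than Clobex and significantly higher than triamcinolone, Locoid and Desowen, each at unadjusted two-sided 5%, with all four required. If any of the four fails, the bracket is not claimed and no single class is assigned.
- Keep the Dunnett-adjusted p-values for stand-alone statements about individual products, and label them so.
- Report the difference between MC2-01 and the Class II cream with its 95% confidence interval, and state that non-significance is not read as showing no difference.
- Restate the joint power for the rule actually used.

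A fallback that assigns the narrowest range of classes the data separate should not be added. It is undefined when MC2-01 is not separated from Clobex, and no error rate is established for it.

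The cost is SAP wording and unadjusted contrasts from the model already planned. The downside is two sets of p-values with different roles, and no class claim when the pattern is incomplete.

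### The SAP makes Dunnett's test primary without revisiting the stated 92% power; naming the step-down version would recover most of the power lost at the planning assumptions, with two trade-offs to state

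*SAP*

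**What the plan says.** Protocol 13.2.1 makes uncorrected 95% intervals for the differences from MC2-01 cream the primary analysis, with Dunnett's test as secondary. Protocol 13.5 sizes the trial to match, using paired t-tests "with 30 complete subjects". There "a maximal standard deviation for the difference of 0.65 is assumed", and the single-comparison result is that "the probability of detecting a difference of 0.5 units assuming a standard deviation for the difference of 0.65 is 98" per cent. It then claims at least 92% "power to obtain 5 significant differences if the true difference with each reference product is at least 0.5". "A total of 36 subjects will be randomized in this trial" to secure the 30.

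The synopsis states the expected pattern. MC2-01 cream is "expected to be lower than Clobex", similar to augmented betamethasone dipropionate, and above the remaining references.

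SAP 5.2.1 changes the primary analysis. If the overall treatment effect is significant, the comparisons are made "with correction for multiplicity using Dunnett's test directly in the primary analysis". SAP 5.4 adds: "All tests will be two-sided and the 0.05 probability level will be chosen to declare significance". The SAP describes its changes to the protocol's methods as minor, does not say whether Dunnett's test is single-step or step-down, and does not restate power. Its results table has one p-value per comparison and no intervals.

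**The concern.** The protocol states its power jointly, for several differences at once. Single-step Dunnett holds all six comparisons to the cut-off that suits the largest of six statistics, even when some are settled almost with certainty; the protocol itself assumes at least 1 point against vehicle. The difficult comparisons are with the neighbours in potency, and these bear the full penalty.

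The step-down form uses the same first cut-off and relaxes it as each hypothesis is rejected. It rejects everything the single-step form rejects, sometimes more, with the same familywise error. At stake is whether the trial keeps roughly the joint power the protocol claimed, and whether the SAP says which test will be run.

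**Working it through.** **1. The protocol's figure.** Inputs from Protocol 13.5: n = 30, difference 0.5, SD of the difference 0.65, two-sided 5%.
- Noncentrality: 0.5 / (0.65/√30) = 0.5 / 0.1187 = 4.21.
- Paired t-test power on 29 df: 98.3% (stated: 98%).
- Five comparisons, multiplied as if independent: 0.9826⁵ = 91.6% (stated: 92%).

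Both figures reproduce. Neither contains a multiplicity correction.

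**2. The SAP analysis.** The subject-by-treatment ANOVA with 30 subjects and 7 treatments has (30 − 1) × (7 − 1) = 174 error df. Comparisons sharing the MC2-01 mean have correlation 0.5 under equal n and a common error variance. This correlation is an assumption that follows from the model; the documents do not state it. Simulated two-sided 5% cut-offs, from six comparisons down to one, are 2.59, 2.54, 2.46, 2.37, 2.23 and 1.97. Single-step applies 2.59 throughout; step-down applies the sequence to the ordered statistics.

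By the protocol's own multiplication method, single-step power per comparison is 94.6%, and 0.9464⁵ = 75.9%. Simulation that respects the correlation gives the figures below.

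**3. Five reference differences of 0.5, vehicle 1, 30 completers.**

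| References above MC2-01 | Single-step | Step-down | Gain (points) |
|---|---|---|---|
| One | 79.5% | 94.2% | 14.7 |
| Two | 78.1% | 94.0% | 15.9 |
| None | 82.5% | 94.5% | 12.0 |

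**4. The hypothesised pattern, true betamethasone difference 0.** The gaps are assumptions. In case (a) Clobex is 0.5 above, the three lower references 0.5 below and vehicle 1 below. In case (c) the gaps are graded: Clobex 0.5 above, the others 0.5, 0.8, 1.3 and 1.8 below. Case (d) is (c) with the two nearest gaps cut to 0.4. *Differences* means all four reference differences plus vehicle are significant. *Full pattern* also requires betamethasone to be non-significant. Each cell shows single-step → step-down.

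| Case | Completers | SD | Differences | Full pattern |
|---|---|---|---|---|
| (a) | 30 | 0.65 | 82.1 → 91.6% | 81.6 → 87.7% |
| (a) | 33 | 0.65 | 88.1 → 94.9% | 87.5 → 90.6% |
| (a) | 36 | 0.65 | 92.3 → 96.9% | 91.6 → 92.4% |
| (a) | 30 | 0.55 | 96.7 → 98.9% | 95.9 → 94.0% |
| (c) | 30 | 0.65 | 89.2 → 95.3% | 88.5 → 90.9% |
| (c) | 36 | 0.65 | 95.6 → 98.3% | 94.8 → 93.7% |
| (c) | 30 | 0.55 | 98.2 → 99.4% | 97.3 → 94.5% |
| (d) | 30 | 0.65 | 57.5 → 74.9% | 57.2 → 72.0% |

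The SD of 0.55 is an assumption, included because the protocol calls 0.65 maximal. The 33 completers come from Protocol 13.4, which expects fewer than 10% of randomized subjects to miss the last visit: 36 × 0.9 = 32.4.

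**5. Error rates.** Over seven null configurations the step-down familywise error was 4.97% to 5.05%, which is 5% within simulation error. With a true betamethasone difference of 0, the chance of declaring one rises from about 1.0% (single-step) to 4.4% in (a) with 30 completers, and approaches 5% as the other comparisons become easier. That rise is why the full-pattern column gains less, or loses.

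**The case against.** **Betamethasone is part of the hypothesis.** Protocol 5.2.2 wants the assay to show no difference from the target-class product, and single-step makes a false difference there less likely. One might infer that single-step gives up power and gets nothing for it. The synopsis hypothesis does not support that, and the full-pattern figures show why. What limits the objection is that low sensitivity to a betamethasone difference is not evidence of similarity. A non-significant result shows no equivalence under either version.

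**The largest gains rest on cautious inputs.** The protocol calls the SD maximal and treats 30 as the minimum number of completers. This stands, and it rules out quoting one gain as if it applied generally. The inputs are nevertheless the ones the protocol's power claim uses.

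**If all comparisons must succeed together, no correction is needed.** Under such a rule uncorrected testing is valid, with about 94–95% power for five reference differences. But neither document sets an all-must-succeed rule; the synopsis states an expectation. The SAP chose familywise control with a separate p-value per reference, and given that choice step-down is the more powerful form of its own test.

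**Single-step is inferred, and it is a valid standard test.** Both true. A reader might take the lower power to mean the SAP analysis is wrong or the trial inadequate. The documents do not support either: familywise error is controlled, and with 36 completers single-step power in (a) is 92%.

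**Intervals.** Single-step has matching simultaneous intervals; step-down has no simple ones. This cost is real, although the SAP results table plans no intervals.

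**Conclusion.** The point holds as an inexpensive improvement and a needed clarification. Read as single-step, the SAP change lowers joint power for five reference differences from the protocol's 92% to about 78–80% when at least one reference lies above MC2-01 (82.5% if none does). Step-down restores it to about 94%. For the four expected differences plus vehicle, case (a), power moves from 82% to 92%, a gain that falls to about 7 points with 33 completers and 5 with 36.

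Counting betamethasone non-significance as success, the gain with 30 completers is about 6 points in (a) and 2 in (c). It is about zero or slightly negative in these cases with 36 completers, and negative with an assumed SD of 0.55. It stays large when the nearest gaps are smaller, about 15 points in (d).

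These figures rest on normality, a common error variance, correlation 0.5 and the assumed gaps. Step-down's lead in the number of differences found, at the same 5% familywise error, does not depend on the gaps. Its size does.

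**What to change.** Before the randomization code is broken, amend SAP 5.2.1 along these lines:

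> Comparisons of MC2-01 cream with the five reference products and the vehicle will use the step-down Dunnett test at a two-sided familywise level of 5%. Significance is judged on the step-down adjusted p-values. Unadjusted 95% confidence intervals for the differences are descriptive; where an interval and an adjusted p-value disagree, the adjusted p-value governs. A non-significant comparison with betamethasone dipropionate will not be interpreted as equivalence.

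Add a row for the intervals to the results table, name the method in its footnote, and restate the joint power for the test chosen.

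The cost is a short SAP edit and a change in the multiple-comparison code, with no extra subjects or data. Two downsides should be recorded: there are no simple matching simultaneous intervals, and the chance of a false betamethasone difference rises from about 1% to 4–5%, within the familywise 5%. If the sponsor prefers single-step for either reason, the SAP should say so and give the lower power figure.
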